5 CRITERIA FOR EVALUATION

5.1 Primary Efficacy Endpoint

Our primary endpoint is number of days experiencing homelessness (with ‘homelessness’ as defined below in section 6.2) during the study period.

For our primary endpoint, number of days experiencing homelessness, given our sample size of 300 with 150 participants in each arm, we estimate that we will have 80% power at a two-sided significance level of 0.05 to detect a mean reduction of 24.0 days in the intervention group, assuming a mean of 52.3 ± 74.0 days experiencing homelessness from prior studies. Allowing for a 27% dropout rate as estimated from prior studies (for a total of sample size of 220 participants with 110 families in each arm), we will still have 80% power at a two-sided significance level of 0.05 to detect a mean reduction of 28.0 days in the intervention group.

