10.11 Early Withdrawal Visit/Assessment

1. Record any Adverse Experiences
2. Concomitant interventions review
3. Record household composition data (number of household members and children).
4. Administer and record current housing situation and history of homelessness instruments, adapted from the Family Options Study and the California Statewide Survey on Homelessness.
5. Administer and record income and employment survey, adapted from the California Statewide Survey on Homelessness.
6. Record concomitant interventions in terms of receipt of assistance from other housing, social, and economic assistance programs.
7. Administer and record monthly expenditure amounts and categories, adapted from the Survey of Income and Participation.
8. Administer and record Financial Well-Being Scale, adapted from the Consumer Financial Protection Bureau (financial well-being).
9. Administer and record Material Hardship Survey, adapted from the Urban Institute Well-Being and Basic Needs and the Survey of Income and Program Participation (material hardship)
10. Administer and record the USDA Brief Food Security Survey (food security)
11. Administer and record healthcare utilization survey, adapted from the California Statewide Survey on Homelessness
12. Administer and record health conditions and functional status survey, adapted from the California Statewide Survey on Homelessness
13. Administer and record Short-Form 12 v2 (physical health)
14. Administer and record Kessler 6 (psychological health)
15. Administer and record the Generalized Self-Efficacy Scale (self-efficacy)
16. Administer and record the Brief Resilience Scale (resilience)
17. Administer and record the Perceived Stress Scale (perceived stress)
18. Administer and record the Confusion, Hubbub and Order Scale (household chaos)
19. Administer and record the Future Scale (aka the Adult Hope Scale) (agency)

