12 DISCONTINUATION AND REPLACEMENT OF PARTICIPANTS

12.1 Early Discontinuation of Study Intervention

A participant may discontinue receipt of the study intervention (guaranteed income) and participation in the evaluation activities at any time if the participant, investigator, or sponsor feel that it is not in the participant's best interest to continue. The following is a list of possible reasons for study treatment discontinuation:

- Participant withdrawal of consent (or assent)
- Adverse event that in the opinion of the investigator would be in the best interest of the participant to discontinue study treatment
- Lost to follow-up
- Sponsor request for early termination of study

If a participant is withdrawn from treatment due to an adverse event, the participant will be followed and treated by the Investigator, study team, and community partners until the issue has resolved or stabilized (i.e., assistance applying for additional public benefits, assistance programs, and/or social services from local, county, state, and federal entities in case of the loss of benefits).

All participants who discontinue the study intervention will be encouraged to undergo an early discontinuation visit/assessment as soon as possible and then should be encouraged to complete all remaining scheduled assessments if possible.

All participants are free to withdraw from participation at any time, for any reason, specified or unspecified, and without prejudice.

Reasonable attempts will be made by the investigator to provide a reason for participant withdrawals. The reason for the participant's withdrawal from the study will be specified in the participant's source documents. Refer to Section 10 for early termination assessment procedures.

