14 STATISTICAL METHODS AND CONSIDERATIONS

Prior to the analysis of the final study data, a detailed Statistical Analysis Plan (SAP) will be written describing all analyses that will be performed. The SAP will contain any modifications to the analysis plan described below.

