14.1 Data Sets Analyzed

All participants who are enrolled, complete a baseline assessment, are randomized, and, for the intervention group, agree to receive GI payments will be included in the modified intention-to-treat analyses. The primary dataset used will be data prospectively collected by the study team via the use of survey instruments and structured interviews as outlined here. We will obtain complementary administrative data on housing status, housing assistance, housing service use, social service use, and health care service use from the Santa Clara Office of Supportive Housing (Homeless Management Information System), Santa Clara Valley Medical Center Hospital & Clinics (Santa Valley Medical Center HealthLink), Santa Clara County Public Health, County of Santa Clara Social Services Agency (including the Department of Employment and Benefit Services), and from community partners (Destination: Home SV, ¡Sí Se Puede! Collective, Sacred Heart Community Service).

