14.3 Analysis of Primary Endpoint

We will conduct modified intention-to-treat analyses to assess our primary endpoint, differences in numbers of days spent homeless using Poisson regression.

Analyses will be adjusted for key demographic and clinical characteristics, including: a) referring organization; b) subtype of homelessness; c) preferred payment disbursement schedule (monthly vs hybrid), as well as for covariates that remain unbalanced across the control and intervention groups after randomization. For missing data, we will use multiple imputation, and will employ the last observation carried forward (LOCF), as a sensitivity analysis to assess the robustness of our multiple imputation approach.

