14.4 Analysis of Secondary Endpoints

We will conduct intention-to-treat analyses to assess our secondary endpoints, using Cox proportional hazards, logistic and linear regression models as appropriate to the endpoint of interest. Analyses will be adjusted for key demographic and clinical characteristics, as well as for covariates that remain unbalanced across the control and intervention groups after randomization. As sensitivity analyses, we will also conduct per protocol analyses for both our primary and secondary endpoint measures. For missing data, we will employ multiple imputation and use the last observation carried forward (LOCF) as a sensitivity analysis to assess the robustness of the LOCF approach.

For our qualitative assessments, we will use a thematic approach with simultaneous data collection and analysis based on modified grounded theory methodologies. We will review interview transcripts and initial analytic memos to develop a preliminary codebook, code transcripts and iteratively discuss with the study team to add or revise existing codes, have two reviewers independently review transcripts and conduct coding, and hold regular study team meetings to discuss emergent themes until reaching consensus.

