14.6 Sample Size and Randomization

Up to 300 eligible participants will be randomly assigned to the guaranteed income group (intervention) or usual care (control group) using a computer-generated randomization scheme developed by the study team. Eligible participants will be referred by the community partners to the study team for consent and enrollment into the study prior to randomization. Once participants are enrolled, they will be randomly assigned to either the intervention or control group. Group assignments will be known to our community partners, who are administering the guaranteed income intervention; however, the study team (investigators and research staff) will be blinded to group assignments.

For our primary endpoint, number of days experiencing homelessness, given our sample size of 300 with 150 participants in each arm, we estimate that we will have 80% power at a two-sided significance level of 0.05 to detect a mean reduction of 24.0 days in the intervention group, assuming a mean of 52.3 ± 74.0 days experiencing homelessness from prior studies. Allowing for a 27% dropout rate as estimated from prior studies (for a total of sample size of 220 participants with 110 families in each arm), we will still have 80% power at a two-sided significance level of 0.05 to detect a mean reduction of 28.0 days in the intervention group.

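### LOCF, the only missing-data sensitivity analysis named for a cumulative day count, is one fixed assumption and says little about robustness to informative dropout

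*Protocol*

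**What the plan says.** Section 14.3 of the protocol analyses days homeless by Poisson regression in a modified intention-to-treat set. Missing data are multiply imputed, and the team "will employ the last observation carried forward (LOCF), as a sensitivity analysis to assess the robustness of our multiple imputation approach". Section 14.4 uses the same pair of methods for the secondary endpoints but describes LOCF "as a sensitivity analysis to assess the robustness of the LOCF approach". It also adds per-protocol analyses of primary and secondary endpoints.

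Sections 5.1 and 14.6 base the sample size on a mean-difference calculation, "assuming a mean of 52.3 ± 74.0 days experiencing homelessness from prior studies". Section 14.6 continues: "Allowing for a 27% dropout rate as estimated from prior studies", which leaves 110 families per arm.

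Other provisions that bear on the point:
- Section 14, on the later statistical analysis plan: "The SAP will contain any modifications to the analysis plan described below".
- Section 12.1: those who stop the intervention "should be encouraged to complete all remaining scheduled assessments if possible".
- Section 10.11 provides an "Early Withdrawal Visit/Assessment".
- Section 12.4(d): families who leave the surveys remain eligible for payments.
- Section 14.1: "We will obtain complementary administrative data on housing status".

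**The concern.** A sensitivity analysis for multiple imputation should show how far the conclusion depends on the assumption about unobserved outcomes. The protocol does not name that assumption; it is presumably missing at random. The useful questions are how much worse the missing families would have to fare before the conclusion changes, and whether that could differ between arms.

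LOCF answers neither. Whether it carries forward the running total, the last interval's days or the last housing status, it puts one assumption in place of another and returns one number. Agreement with multiple imputation could be read as evidence of robustness when no departure of interest has been examined. Disagreement could be read as a fault in the imputation when it comes from LOCF itself. The per-protocol analyses do not fill the gap, because they change who is analysed and not what is assumed about missing days.

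What is at stake is the credibility of the robustness statement that will accompany the primary result, not the primary result itself.

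**Working it through.** **Inputs from the protocol (5.1, 14.6):** SD 74.0 days; control mean 52.3; detectable reductions 24.0 (150 per arm) and 28.0 (110 per arm); two-sided 0.05; dropout allowance 27%.

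**Assumptions added here:** 27% missing in each arm; multiple imputation returns the planned difference; missing intervention families have δ more homeless days than imputed; controls are not shifted; the standard error is held fixed. The planned model is Poisson, so this shows size only.

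**1. The plan's own figures reproduce.** SE = 74.0 × √(2/n), normal approximation.
- n = 150: SE = 8.545; 24.0/8.545 gives power 80.2%.
- n = 110: SE = 9.978; 28.0/9.978 gives power 80.1%.

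**2. Tipping points, using the protocol's own pairings.** Shifted difference = Δ − 0.27δ. Significance is lost when this equals 1.96 × SE, so δ = (Δ − 1.96 × SE)/0.27.
- Δ = 24.0, n = 150: (24.0 − 16.748)/0.27 = 7.252/0.27 = 26.9 days.
- Δ = 28.0, n = 110: (28.0 − 19.557)/0.27 = 8.443/0.27 = 31.3 days.
- The whole difference disappears at 24.0/0.27 = 88.9 or 28.0/0.27 = 103.7 days.

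**3. Scale.** The assumed intervention mean is 52.3 − 24.0 = 28.3 days in the first case and 52.3 − 28.0 = 24.3 in the second. The shifts are 26.9/28.3 = 95% and 31.3/24.3 = 129% of those means. Missing families would need roughly twice their arm's expected total, or a little more.

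**4. Less missing data.** At 10% missing, with Δ = 24.0 and SE 8.545, the tipping point is 7.252/0.10 = 72.5 days.

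**5. Why the arms must be shifted separately.** The same δ in both arms changes the contrast by 0.27δ − 0.27δ = 0. Only a differential shift tests the treatment effect.

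**6. What LOCF returns when imputation is right.** Assume that every family is homeless at entry and exits without return, with arm means 52.3 and 28.3. Assume also 27% dropout unrelated to outcome, with families last seen equally often at months 6, 12, 18, 24, 27 and 30. The true difference is 24. Over three exit-time shapes (gamma with SD 74 in both arms, gamma with equal coefficient of variation, exponential) LOCF gives:
- running total: 23.7 to 24.1
- last status: 24.8 to 26.1
- last interval's rate: 28.9 to 29.5
- last interval's count: 30.0 to 30.6

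If nobody is last seen before month 12, all four versions lie between 23.9 and 25.3. The gap from multiple imputation therefore depends on what is carried forward and on how early families leave. It does not measure informative dropout.

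**The case against.** The strongest reply is that a detailed statistical analysis plan is promised, that it may modify the protocol, and that tipping-point imputation is routine content for it. This stands in part: the protocol does not call LOCF exclusive, and how LOCF would be set up can be left to that plan. But the protocol does name a tool and gives it the job of showing robustness, and that choice can be judged now.

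A reader might infer four stronger things, which the documents do not support.
- *That LOCF is disqualified because it uses only data before dropout.* Every missing-data method does, including delta adjustment at any given δ. The valid complaint is that LOCF supplies one assumption and no graded range.
- *That the result is highly fragile.* Pairing a 24.0-day effect with 110 per arm gives a tipping point of about 16 days, but the protocol pairs 110 with 28.0 days, which gives 31. Setting 27 days against all the follow-up a family has left also makes the shift look small, when it nearly equals the assumed 28.3-day intervention mean.
- *That LOCF will raise false alarms.* The excess is at most 30.6 − 24 = 6.6 days, below one standard error, and it shrinks to about 1.3 when nobody is last seen before month 12.
- *That 27% of follow-up will be missing.* The figure is a sample-size allowance. The early-withdrawal assessment, continued follow-up after stopping the intervention and administrative housing data should all reduce missing data. Continued payments under 12.4(d) mean that leaving the surveys need not mean losing the intervention, which weakens the case for an adverse shift in that arm alone.

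These points bear on which shifts are plausible. They do not make LOCF able to explore them.

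**Conclusion.** The point holds in limited form. As the only named missing-data check on multiple imputation of a cumulative day count, LOCF is a weak choice, and its agreement or disagreement with the primary analysis would say little about informative dropout. The primary estimate, test and power do not change, and it does not follow that no better analysis will be done.

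The figures a useful sensitivity analysis would report are of the order of 27 extra days (24.0-day effect, 150 per arm) or 31 (28.0-day effect, 110 per arm). They rest on 27% missing per arm, a shift in the intervention arm only, a fixed standard error and the mean-difference scale. Such shifts are large against the assumed intervention means, so the result may prove robust; the named analysis could not show it. The wording in 14.4, where LOCF is said to test LOCF, does not fit 14.3 and is probably a drafting slip. The change is worth making but is not critical.

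**What to change.** Keep multiple imputation as the primary method. In 14.3 and 14.4, or in the statistical analysis plan as section 14 allows, replace LOCF or demote it to supplementary. Put in its place delta-adjusted multiple imputation of homeless days per assessment interval; for secondary endpoints, impute the relevant outcome. Scale the shift to interval length, since assessments are three or six months apart. Vary it separately by arm until the conclusion changes, and report that tipping point. Use the administrative housing data already planned in 14.1 to judge which shifts are plausible, taking account of the continued payments under 12.4(d).

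Correct 14.4 so that the sensitivity analysis assesses the multiple-imputation approach.

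The cost is a wording change and modest extra programming. No new data are needed.

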14.4 Analysis of Secondary Endpoints

We will conduct intention-to-treat analyses to assess our secondary endpoints, using Cox proportional hazards, logistic and linear regression models as appropriate to the endpoint of interest. Analyses will be adjusted for key demographic and clinical characteristics, as well as for covariates that remain unbalanced across the control and intervention groups after randomization. As sensitivity analyses, we will also conduct per protocol analyses for both our primary and secondary endpoint measures. For missing data, we will employ multiple imputation and use the last observation carried forward (LOCF) as a sensitivity analysis to assess the robustness of the LOCF approach.

For our qualitative assessments, we will use a thematic approach with simultaneous data collection and analysis based on modified grounded theory methodologies. We will review interview transcripts and initial analytic memos to develop a preliminary codebook, code transcripts and iteratively discuss with the study team to add or revise existing codes, have two reviewers independently review transcripts and conduct coding, and hold regular study team meetings to discuss emergent themes until reaching consensus.

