4 STUDY DESIGN

4.1 Study Overview

This is a single-site, single-blinded randomized controlled trial. The community partner service organizations, Destination: Home SV and the ¡Sí Se Puede! Collective, have raised funds to provide unconditional cash assistance in the form of guaranteed income (GI) for a period of two years to 150 families with children experiencing homelessness in Santa Clara County and who are eligible for referral to rapid rehousing assistance programs (RRH). The partner service organizations are prioritizing assistance to those awaiting RRH referral given the current extended wait time for RRH services. Because there are far more families who are eligible for GI than there are available resources, 150 eligible families will be randomly selected to receive GI. From the pool of eligible families, we will also randomly select an additional 150 participants as matched controls for the purpose of evaluation.

Thus, we are planning for a total of 300 participants. Participants will be assigned to either the control (usual care) or intervention (guaranteed income) groups in random order. Evaluations will be taken at baseline and every 6 months monthly via in-person and/or telephone assessments.

Screening data will be reviewed to determine participant eligibility. Participants who meet all inclusion criteria and none of the exclusion criteria will be entered into the study.

The following treatment regimens will be used:

- Intervention – guaranteed income, consisting of a total of \$24,000 to be disbursed over 24 months. Participants may opt for either monthly (\$1,000/month) or hybrid (lump sum of \$6,500 the first month, then \$500/month x 11 months for a total of \$12,000 per

year) disbursement schedules, with the option to switch disbursement schedule after the first 12 months. Participants will also be invited to attend a Public Benefits Information Session to learn about public benefits and social assistance programs available to residents of Santa Clara County. Participation in this Benefits Information Session will be optional and not required for study participation.

- Control – usual care as per the partner service organizations. Participants will be invited to also attend a Public Benefits Information Session to learn about public benefits and social assistance programs available to residents of Santa Clara County. Participation in this Benefits Information Session will be optional and not required for study participation.

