7 CONCURRENT INTERVENTIONS

All participants will maintain eligibility for all other available housing, social, and economic assistance programs. Participants will not be excluded from receipt of any other housing assistance (nor any other assistance programs) should any be available to them during the study period.

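### The planned per-protocol sensitivity analysis has no stated set; if the set rests on receipt of payments, exclusions fall on the cash arm alone and the analysis cannot by itself show robustness

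*Protocol*

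**What the plan says.** Section 14.4 of the protocol commits to an additional analysis and gives it a purpose: "As sensitivity analyses, we will also conduct per protocol analyses for both our primary and secondary endpoint measures". The sentence sits under secondary endpoints but covers the primary endpoint too. No section says which families form the per-protocol set. Section 14 leaves detailed description of the analyses to a later SAP.

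Four other provisions bear on who could be excluded:

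- **Control condition (section 4.1).** "Control – usual care as per the partner service organizations". The one extra offered to both arms is a benefits session, of which the plan says "Participation in this Benefits Information Session will be optional and not required for study participation".
- **Other assistance (section 7).** "Participants will not be excluded from receipt of any other housing assistance". This applies to both arms.
- **Stopping (section 12.1).** "A participant may discontinue receipt of the study intervention (guaranteed income) and participation in the evaluation activities at any time".
- **Violations (section 13).** The only example listed is failure to meet the eligibility criteria. The list is expressly open-ended.

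The reference analyses differ by endpoint. For the primary, section 14.3 states: "We will conduct modified intention-to-treat analyses to assess our primary endpoint, differences in numbers of days spent homeless using Poisson regression". Section 14.1 admits to that set families who enroll, complete baseline, are randomized and, "for the intervention group, agree to receive GI payments will be included in the modified intention-to-treat analyses". For the secondary endpoints, section 14.4 states: "We will conduct intention-to-treat analyses to assess our secondary endpoints".

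**The concern.** A sensitivity analysis should ask the same question as the main analysis under different assumptions, so that agreement between the two is informative. A per-protocol set built on receipt of payments does not do this. Non-receipt is possible only in the cash arm, because controls are offered nothing that they could decline or stop. Taking non-receivers out of one arm after randomization leaves a selected group facing an unselected one, and their difference mixes the effect of cash with the reasons for stopping.

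Those reasons may be related to housing. Section 12.1 lists adverse events and loss to follow-up among the reasons for discontinuation. Section 11.1 names loss of public benefits as a main adverse event of concern. Section 12.4(c) makes continued payment to families who leave the county depend on current contact details.

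What is at stake is interpretation. For the primary endpoint the modified intention-to-treat set already leaves out cash-arm decliners with no counterpart among controls. A receipt-based per-protocol set would remove a second group from the same arm. If decliners and stoppers both fare worse than average, both analyses err in the same direction, and agreement between them gives false reassurance.

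**Working it through.** **1. Where each possible criterion can act**

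| Possible ground for exclusion | Cash arm | Control arm | Source |
|---|---|---|---|
| Declined or stopped payments | yes | not possible | 4.1, 12.1 |
| Skipped the benefits session | not a deviation | not a deviation | 4.1 |
| Used other assistance | not a deviation | not a deviation | 7 |
| Failed eligibility | yes | yes | 13 |
| Left the study or missed assessments | yes | yes | 12.2, 10 |

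Only the first row is one-sided. Eligibility failure, if judged on data from before randomization, can be applied to both arms without breaking the comparison.

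**2. What a receipt-based set would add**

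- Primary endpoint: decliners are already out under section 14.1, so only families who stop after agreeing would be removed.
- Secondary endpoints: the reference is intention-to-treat, so both decliners and stoppers would be removed.

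**3. The plan's own figures**

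Inputs from sections 5.1 and 14.6: mean 52.3 days, SD 74.0, two-sided 0.05. Normal approximation, power = Φ(δ/SE − 1.96), with SE = 74.0 × √(2/n).

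- n = 150 per arm, δ = 24.0: SE = 8.54, power = 80.2%.
- n = 110 per arm, δ = 28.0: SE = 9.98, power = 80.1%.

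Both stated 80% figures reproduce, so mean, SD and target can serve as the scale for what follows.

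**4. Size of the bias under assumed rates**

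Assume no true effect and a mean of 52.3 days in both full arms. If a share p of cash families with mean m is dropped, the retained mean is (52.3 − p × m)/(1 − p).

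- p = 0.05, m = 120: 46.3/0.95 = 48.7, a shift of −3.6 days.
- p = 0.10, m = 120: 40.3/0.90 = 44.8, a shift of −7.5 days.
- p = 0.10, m = 150: 37.3/0.90 = 41.4, a shift of −10.9 days, which is 45% of 24.0.

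The same bias can be written as −q × D, where q is the share dropped and D is the excess of the dropped families' mean over that of the retained. With 150 controls, SE = 74 × √(1/150 + 1/(150(1 − q))). The last column is the two-sided rejection rate with no true effect.

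| q | D (days) | Bias (days) | Share of 24.0 | Rejection rate |
|---|---|---|---|---|
| 2% | 37 | −0.7 | 3% | 5.1% |
| 5% | 74 | −3.7 | 15% | 7.1% |
| 10% | 37 | −3.7 | 15% | 7.1% |
| 10% | 74 | −7.4 | 31% | 13.5% |
| 20% | 74 | −14.8 | 62% | 37% |
| 10% | −37 | +3.7 | 15% | 7.1% |

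Neither p and m nor q and D come from the protocol. The calculation compares means, as the sample-size statement appears to do, and not through the planned Poisson model.

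**5. Why an instrumental analysis avoids this**

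Controls have no access to the payments, so the complier effect is the full intention-to-treat difference divided by the share of the cash arm counted as receiving. With no true effect and 90% receipt (assumed), this is 0/0.90 = 0, whatever the prognosis of the other 10%. The price is precision: the standard error grows by roughly 1/0.90, from 8.54 to about 9.5 days.

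**The case against.** The strongest reply is that the protocol never says the per-protocol set depends on receipt. Defining analysis sets is commonly left to the SAP, which is not at hand, and the only violation listed can occur in either arm. Study withdrawal and missed assessments can also occur in both. This stands, and it makes the point conditional. It does not remove the point, because the protocol itself fixes the choice of analysis and its label. A set based on eligibility alone would be a fair comparison but would say nothing about robustness to non-receipt.

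A second reply is that non-receipt may be rare. Section 12.4 keeps payments going after incarceration (through a secondary payee), family separation, a move out of the county, and withdrawal from the surveys. This also stands, and it limits the likely size of the bias.

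A reader might go further and infer that the per-protocol result is certain to be confounded, or that it will favor cash. The documents support neither. The first needs a receipt-based set, which is not stated. The second needs stoppers to be worse housed, which no section says. Families who stop in order to protect public benefits need not be the worst off, and the bias reverses if they fare better. Nor does any section say that the per-protocol result would be presented as support for the primary result.

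**Conclusion.** The point holds in conditional form. The protocol commits to per-protocol analyses as sensitivity analyses without saying who is in the set. If the set is based on receipt, exclusions for non-receipt can occur only in the cash arm, and the result cannot by itself show that the main finding is robust. For the primary endpoint this would come on top of the one-arm exclusion written into section 14.1, so the analysis being checked is not a comparison of all randomized families either.

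The size and direction of any bias are unknown. The 3.6 to 10.9 days rest on assumed shares of 5 to 10% and assumed means of 120 to 150 days, 2.3 to 2.9 times the planned 52.3. With 2% dropped and a 37-day difference, the bias is 0.7 days and can be ignored. This is a low-cost improvement to a secondary analysis and does not undermine the trial.

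**What to change.** Amend section 14.4, or settle the following in the SAP before unblinding:

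1. Do not exclude families for non-receipt in a per-protocol set. Limit any per-protocol exclusions to criteria that apply equally to both arms, such as eligibility failure judged on pre-randomization data, and label that analysis supplementary.
2. Report a full intention-to-treat analysis of all randomized families, including cash-arm decliners, as the reference.
3. To address non-receipt, estimate a complier average causal effect in the same families, with assignment as the instrument. Prespecify a binary definition of receipt taken from the payment administrator's data, and state the scale of the estimate (for example, difference in mean days). Use the primary model's covariates, provided they were recorded before randomization. The share of payments received should enter only as a dose-response variant, because it needs a different interpretation.

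The cost is mainly wording. Section 14.1 already names the payment administrator as a data source, although it does not list payment records, so their availability should be confirmed. Outcomes for decliners must be collected or imputed. The interval will be wider. The method also assumes that assignment acts only through the payments. Participants are not blinded, and section 2.1 acknowledges disappointment at not being selected, which could strain that assumption and should be stated with the result.
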